5.7.2. Laboratory, Vital Signs and Physical Examination

Coagulopathy laboratory values will be listed. A listing of all other laboratory values will be made, restricted to participants with at least one laboratory abnormality.

Physical examination findings will be summarized at baseline. A listing of the abnormalities will be made.

Vital signs including temperature, pulse/heart rate, respiratory rate, and blood pressure (systolic and diastolic) will be summarized over time, using descriptive statistics.

Abnormalities emerging after vaccination will be tabulated by worst abnormality grade using the FDA table in Section 6.8 and in Section 6.9.

An abnormality (toxicity grade or abnormality based on normal ranges) will be considered as emerging in a particular period if it is worse than the baseline value. If the baseline is missing, the abnormality is always considered emerging. A shift from ‘abnormally low’ at baseline to ‘abnormally high’ post baseline (or vice versa) is also considered emerging. In case a laboratory test result is censored (no numeric value is available, but only a verbatim term) then a numeric value will be imputed by a value exceeding the cut-off value with one unit. (<x: subtract 1 unit from x, >x: add 1 unit to x; <3.45 is imputed with 3.44).

In case no toxicity grades are defined for a test, the abnormalities (above/below normal range) will be used. In determining toxicity grades, the following rules are applied:

- Worst grades/abnormalities are determined over the whole observational period for each trial period separately, including all post-baseline measurements of that period.
- The abnormalities ‘abnormally low’ and ‘abnormally high’ are considered equally important, i.e. if a participant has as well an abnormally low as an abnormally high value post-baseline, both abnormalities are shown in the tables. (This means that the sum of the percentages can be more than 100%).

- Note: as the grading scale for some parameters in the grading table has some gaps (zones where no toxicity grade definition exists), laboratory results falling in these zones will be allocated to the adjacent worst-case grade.
- If a laboratory value falls within the grading as specified in the grading table but also within the local lab normal limits, the value is considered as normal.

For the grades, no distinction will be made between test results of samples obtained under fasting and under non-fasting conditions: in case limits under fasting and non-fasting conditions differ, the limits of the conditions (fasting/non-fasting) of scheduled visits as planned in the CTP will always be used, also for samples obtained under a different condition (e.g. samples of withdrawal visits).

Change from baseline in laboratory results (shift table based on toxicity grade) will be summarized by timepoint post vaccination.

A listing of participants with fever according to the FDA grading table will also be provided. In addition, temperature measurements (whether obtained from the diary or from on-site assessments) will be allocated to predefined temperature intervals (from 37.5° C until 40°C, in steps of half degree increments; e.g. <37.5, 37.5-<38, 38-<38.5, ... >40), and the worst temperature reported over the first 7 first days after a vaccination (Day1 to Day8, from any of the diary or the on-site assessments) will be tabulated by intervals.

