Solicited AE recording		Continuous		Continuous						Continuous												
Unsolicited AE recording ^o		Continuous (Day 28)			Continuous (Day 28)						Continuous (Day 28)											
MAAE recording ^p										Continuous												
SAE/AESI recording ^q										Continuous												
Concomitant meds ^r										Continuous												
Participant reactogenicity diary dispensation and review ^s		●	●				●			●					● ⁴							
eCOA training and set up ^t		●																				
Nasal swab and saliva collection training ^u		●																				
Training on AESI symptoms		●																				
Distribution of rulers, thermometers, and SIC reference card		●																				
SIC, including body temperature of the participant (PROs to be completed by the participant in the eCOA) ^v		● ¹																				
(Suspected) COVID 19 surveillance (symptom check) ^w										Continuous												

Phase	Screening	Study Period	3	4	5	6	7	8	At approximately 6 months of study participation	9	10	11	12	13	Exit ^b
Visit #	1	2	3	4	5	6	7	8		Vac 1 + 7 d	Vac 1 + 28 d	Vac 1 + 56 d	Vac 2 + 7 d	Vac 2 + 14 d	Vac 2 + 28 d
Visit Timing ^a		Vac 1	Vac 1 + 7 d	Vac 1 + 28 d	Vac 1 + 56 d	Vac 2 + 7 d	Vac 2 + 14 d	Vac 2 + 28 d		Vac 1 + 6 m	Vac 3 + 7 d	Vac 3 + 14 d	Vac 3 + 28 d	Vac 3 + 6 m	
Target Visit Day ±Window	-28 to 1	1	8±2 ^c	29±3	57-3±7	64*±2 ^c	71*±2	85*±3		Day 184±30 **	Day 191* ±2 ^c	Day 198*±3	Day 212*±3	Day 366* ±21	
Visit Type	Screening	Vaccination 1	Safety	Safety (and immuno)	Vaccination 2	Safety	Safety (and Immuno)	Safety		Vaccination 3	Safety	Safety (and Immuno)	Safety	Safety (and Immuno)	
AESI reminder ^x		Daily for 30 days after vaccination		Daily for 30 days after vaccination				Daily for 30 days after vaccination							

●¹ pre-vaccination; ●² pre- and post-vaccination; ●³ blood samples for immunogenicity will only be taken if the early exit visit is at least 10 days after the previous immunogenicity blood draw; ●⁴ if within 7 days of the previous vaccination

*The timings of visits after the second and third vaccinations will be determined relative to the actual day of that vaccination, respectively.

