10.2. Appendix 2: AESI Clinical Laboratory Tests

Samples will be taken according to the SoA in Section 1.3. The following tests may be performed:

Protocol-Required AESI Laboratory Assessments

Laboratory Assessments	Parameters for Participants Evaluated at Prespecified Study Timepoints and, in Addition, upon Experiencing a Suspected AESI
Performed locally (or centrally if local laboratory is not available)	
	Blood sample obtained and tested at study Day 1, Day 29, Day 57, Day 71 (for all participants), for visits Day 184 and Day 198 (for Groups 1-3), AND Day 1/29 for each occurrence of any suspected AESI (TTS and/or MIS-C)
Hematology	Whole blood sample for platelet count which at some sites may be part of a complete blood count with differential.
Suspected TTS AESI	
Stored and performed centrally	
Only analyzed if participant experienced suspected TTS, upon request from central study team: Blood sample obtained at Day 1/29 for each occurrence of suspected TTS AESI and for visits Day 1, Day 29, Day 57, Day 71 (for all participants), for visits Day 184 and Day 198 (for Groups 1-3)*.	
Clinical Laboratory Assessments (Section 8.2.4.1)	
Serum/plasma samples for coagulation-related assays such as but not limited to:
 
 • Activated partial thromboplastin time • Prothrombin time • International normalized ratio • Fibrinogen • Lupus anticoagulant • Beta-2 glycoprotein • Anti-cardiolipin • D-dimers • Anti-PF4 • Heparin Induced Thrombocytopenia (HIT)/PF4 Ab, IgG·(HIT assay) • Platelet activation assay (if HIT/PF4 is positive) • Homocysteine • ADAMTS13 Activity and Inhibitor Profile

Laboratory Assessments	Parameters for Participants Evaluated at Prespecified Study Timepoints and, in Addition, upon Experiencing a Suspected AESI
Suspected MIC-S AESI Stored and performed centrally: Only analyzed if participant experienced suspected MIS-C, upon request from central study team: Blood sample obtained at Day 1/29 for each occurrence of suspected MIS-C AESI and for visits Day 1, Day 29, Day 57, Day 71 (for all participants), for visits Day 184 and Day 198 (for Groups 1-3)*.	
Clinical Laboratory Assessments (Section 8.2.4.2)	
 • Serum/plasma samples for coagulation-related assays such as, but not limited to, D-dimers • Levels of inflammatory markers in the blood, including elevated ESR/CRP and ferritin, LDH, and ALC • B-type natriuretic peptide (BNP) or NT-proBNP (pro-BNP) • Sodium

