5. STATISTICAL ANALYSES

5.1. General Considerations

Details of the vaccine schedules associated to the primary vaccine regimen will be provided in the data presentation specification (DPS) document. Vaccination schedule have 2 components:

- Primary Vaccine Regimen (1-active dose or 2-active dose)
- Booster Vaccination (i.e. after unblinding)

Unless specified otherwise, analyses outputs will be produced by age group (12 to 15, 16 to 17, and overall). Where applicable, output will include results by dose level (1-active dose regimen and 2-active dose regimen combined) to report the post-dose 1 period.

All safety and immunogenicity data after a participant has received any other SARS-CoV-2 vaccine not part of the protocol will not be tabulated. Those data will be in listings.

A baseline (or reference) value will be defined as the value of the last available assessment prior to the first vaccination on Day 1, unless specified otherwise.

Unless otherwise stated, safety analyses will be conducted on the FAS, Immunogenicity analyses on the PPI.

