5.8.1.4. Immunogenicity Against the Insert

5.8.1.4.1. Humoral assays

The seroresponse rate of S-ELISA (or equivalent assay, e.g. MSD), and the VNA will be reported as the proportion of participants with either:

- a baseline sample value of less than or equal to the lower limit of quantitation (LLOQ; [\leq LLOQ]) and a postbaseline sample strictly greater than the LLOQ ($>$ LLOQ), or
- a baseline sample value strictly greater than the LLOQ ($>$ LLOQ) and a postbaseline sample value representing an at least 4-fold (\geq 4-fold) increase from the baseline sample value.

In addition, the following definition of seroresponse rate of the VNA (and possibly S-ELISA or equivalent assay e.g. MSD) will be reported as an exploratory endpoint: the proportion of participants with at least 4-fold increase from the baseline sample value, where a baseline sample value of less than or equal to the lower limit of quantitation will be set to LLOQ for the analysis.

For S-ELISA and VNA (both wild-type virus and pseudovirion expressing S protein, as available) assays, the following results will be calculated: N, geometric mean and corresponding 95% CI of

the actual values and fold increases from baseline and from pre-dose 2 or pre-dose 3 (for time points after dose 2 and time points post booster, respectively) will be tabulated and graphically presented.

For the calculation of the geometric mean and its corresponding 95% CI, the arithmetic mean and its corresponding 95% CI are calculated on the \log_{10} transformed values. These values are back transformed to provide the geometric mean and its corresponding 95% CI.

Actual values are tabulated and shown as dot plots with dots for participant values, and the corresponding geometric mean and 95% CI per time point for each assay. In addition, GMT (VNA) or GMC (S-ELISA or equivalent assay, e.g. MSD) plots over time, combining the regimens in one graph (without individual participant dots) will also be generated.

Participant profiles of the actual values over time will be graphically presented. In the graphs, original values will be displayed on the \log_{10} scale. Reverse distribution curves of the actual values will be provided for selected time points. Further details and/or updated rules will be provided in the DPS.

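### A laboratory or vital-sign abnormality that begins after dose 1 and persists is counted again as emerging after dose 2 and after the booster, because every period is judged against the value before the first vaccination

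*SAP*

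**What the plan says.** SAP 5.7.2 calls an abnormality emerging when it is worse than baseline: it "will be considered as emerging in a particular period if it is worse than the baseline value". Grades are taken period by period: "Worst grades/abnormalities are determined over the whole observational period for each trial period separately". A missing baseline has its own rule: "If the baseline is missing, the abnormality is always considered emerging".

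SAP 5.1 fixes the reference: "A baseline (or reference) value will be defined as the value of the last available assessment prior to the first vaccination on Day 1". That sentence allows exceptions where stated, but 5.7.2 states none. SAP 5.1.2 presents safety results by phase and period, and Table 3 in SAP 5.1.3 makes Post-dose 1, Post-dose 2 and Post-dose 3 (the booster) separate periods. The laboratory shift table in 5.7.2 is by time point, but it too measures change from baseline.

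A later reference is available. Protocol Appendix 2 (10.2) schedules the hematology sample as follows: "Blood sample obtained and tested at study Day 1, Day 29, Day 57, Day 71 (for all participants), for visits Day 184" and Day 198, the last two for Groups 1-3. The Schedule of Activities (Protocol 1.3.1 and 1.3.2) marks the Day 57 and Day 184 samples as taken before vaccination. It marks vital signs at the vaccination visits as "pre- and post-vaccination".

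Elsewhere the SAP does use dose-specific references. Immunogenicity is reported as "fold increases from baseline and from pre-dose 2 or pre-dose 3" (SAP 5.8.1.4.1), and adverse events are allocated to the period in which they start (SAP 5.7.1.4).

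**The concern.** A reader of a table of abnormalities emerging in the Post-dose 2 or Post-booster period will take it to show what appeared or worsened after that injection. Under the rule it shows something else: anything worse than before any study vaccine, whenever it began. An abnormality that arose after dose 1 and did not change is repeated in each later period in which it is measured.

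At stake is how the by-period safety tables read. In Groups 1-3 the second injection is saline, so a persisting dose 1 change would appear in the period after saline. After the booster, no unboosted group is followed on the same schedule, so nothing in the table helps a reader separate old changes from new ones.

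**Working it through.** The plan gives no figure on this point, so there is none to reproduce. The check is a trace of the rule, followed by illustrations whose inputs are assumptions.

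**1. Age of the reference, from the target days**
- Post-dose 2 laboratory sample: Day 71. Days since the Day 1 reference: 71 − 1 = 70. Days since the pre-dose sample: 71 − 57 = 14.
- Post-booster laboratory sample: Day 198. Days since Day 1: 198 − 1 = 197. Days since the pre-dose sample: 198 − 184 = 14.

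**2. Trace of one participant in Groups 1-3**

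Take a blood-count parameter that is normal on Day 1 and Grade 1, unchanged, at every later sample.

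| Sample | Period | Against Day 1 | Against last pre-dose value |
|---|---|---|---|
| Day 29 | Post-dose 1 | emerging | emerging (same reference) |
| Day 57, pre-dose | Follow-up 1 | emerging | not applicable |
| Day 71 | Post-dose 2 | emerging | not emerging (Day 57 was Grade 1) |
| Day 198 | Post-booster | emerging | not emerging (Day 184 was Grade 1) |

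The case is counted where it began and then repeated. If the Day 1 value is missing, the Day 71 and Day 198 abnormalities count as emerging even though pre-dose values exist.

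**3. Size per case**

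One participant in a group of 50 is 1/50 = 2 percentage points.

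**4. Expected repeat counts if vaccination 2 has no effect**

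Let p be the share with a new abnormality between Day 1 and the Day 57 pre-dose sample, and q the share of those still abnormal on Day 71. Both are assumptions. The expected repeat count is n × p × q. With n = 50 and q from 50% to 100%:
- p = 5%: 1.25 to 2.5 participants
- p = 10%: 2.5 to 5 participants
- p = 20%: 5 to 10 participants

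With the Day 57 reference and no worsening, each of these is 0.

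**5. Persistence or random fluctuation?**

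A simulation with no vaccine effect used normally distributed values at Days 1, 57 and 71 and an abnormality threshold at the lowest 5%.

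| Correlation Day 57–71 | Correlation of Day 1 with each | Emerging on Day 71, Day 1 reference | Emerging on Day 71, Day 57 reference |
|---|---|---|---|
| 0.7 | 0.7 | 3.04% | 3.03% |
| 0.8 | 0.6 | 3.49% | 2.57% |
| 0.9 | 0.6 | 3.46% | 1.81% |

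With equal correlations the choice of reference makes no difference. The excess appears only when Day 71 resembles Day 57 more than Day 1, that is, when changes that began before Day 57 persist.

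**6. Effect on the contrast between active and saline second doses**

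Let c = p × q be the carry-over share, equal in both arms, and let a and s be the shares newly abnormal after active and saline. Assume that new abnormality is unrelated to carry-over and that each participant is counted once per period. The tabulated rates are c + (1 − c)a and c + (1 − c)s, and their difference is (1 − c)(a − s). For p = 5% and q = 50%, c = 2.5% and the difference is multiplied by 0.975. For p = 10% and q = 100%, c = 10% and the factor is 0.90. The contrast shrinks but keeps its direction.

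**The case against.** The case for leaving the rule alone has real force.

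- **The endpoints are not affected.** The primary and secondary safety endpoints are solicited and unsolicited adverse events, medically-attended events, serious events and events of special interest. They are dated by onset or tied to their own dose. Laboratory and vital-sign grades fall under other safety analyses, and all safety analysis is descriptive. This stands.
- **Platelets have a second route.** Grade 1 starts at 140,000 and below (SAP 6.9), while any count below 150,000/µL is a suspected event of special interest with its own reporting and follow-up. A persisting platelet fall would be dated to dose 1 there. This stands for platelets. It does not cover other blood-count parameters or vital signs.
- **Onset can be traced.** Listings and the by-time-point shift table show abnormal grades at Day 57. This stands in part: the shift table starts from baseline, so it does not show movement from Day 57 to Day 71 within participants, and it covers laboratory values only.
- **The arms share the carry-over.** Randomised groups receive the same virus-particle levels at dose 1, although Groups 1 and 4 differ in volume. A reader might infer that the comparison of active with saline second doses is invalid. The documents do not support that: the saline arms display the background, and the contrast is at most diluted.
- **Emerging is a timing label.** A reader might infer that the SAP attributes old abnormalities causally to saline or to the booster. It does not; they are counted in their true period and repeated later.
- **The reverse pattern is defensible.** Someone with Grade 1 on Day 1, normal on Day 57 and Grade 1 again on Day 71 is not counted. That participant is no worse than before any study vaccine, and leaving the case out is an accepted convention.
- **Day 1 is the only value free of study vaccine.** This stands, and is why that reference should remain.

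**Conclusion.** The point holds as a minor one. By its wording, SAP 5.7.2 counts a persisting abnormality that began after dose 1 again in the Post-dose 2 and Post-booster periods. The effect is confined to descriptive supportive tables, chiefly platelet or blood counts and vital signs; the central coagulation tests are run only for a suspected event of special interest. No test or error rate is involved.

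It matters most for the booster period in Groups 1-3, where there is no concurrent control and the reference is about 6 months old.

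The size cannot be taken from the documents. Each persisting case adds 2 percentage points in a group of 50. The expected counts and simulated rates above depend on assumed values for onset, persistence and correlation, and the excess vanishes if changes do not persist. The conclusion also assumes that the Data Presentation Specifications, which are not among the documents, set no other reference.

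**What to change.** In SAP 5.7.2, keep the Day 1 reference and add that, for the Post-dose 2 and Post-booster periods, emergence and the laboratory shift table will also be given against the last value before that vaccination (the Day 57 or Day 184 pre-dose assessment). Show the two versions side by side. Where the Day 1 value is missing, use that pre-dose value for these periods instead of counting every abnormality as emerging.

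Pre-dose readings should be identified by their scheduled pre-vaccination label. SAP 5.1.2 sets a missing vaccination time to 00:00, which would otherwise move a same-day pre-dose reading into the post-dose period.

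The change needs no new data. It costs a sentence or two in the SAP, repeat tables and two references to explain. The pre-dose value may itself reflect an earlier dose, so using it alone would hide cumulative change; that is why it should supplement the Day 1 comparison and not replace it.

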5.8. Other Analyses

5.8.1. Immunogenicity Analyses

The analysis of immunogenicity will use the PPI set. Immunogenicity analyses will also be done on the FAS (participants who became infected during the study will be analyzed as a subgroup and shown in the graphs using different colors and symbols). Data will be analyzed by vaccination schedule, age group. Key immunogenicity assay results will also be analyzed for the subgroups defined in Section 5.8.5.

Data will be presented by scheduled time point. For the PPI analysis, samples taken outside of the allowed window will be excluded from the tables and graphs (but will be included in the listings and clearly marked as results not included in the PPI analyses). For the FAS analysis, samples taken outside of the allowed window will be included. Key immunogenicity assay data from other studies, which are used to benchmark results from this study, will also be generated. Reference to the respective study will be added to those tables and graphs.

Note: analyses that are potentially unblinding at the individual participant level (e.g. graphs showing individual data tied to COVID-19 infection status, especially when the number of COVID-19 infections is low and/or when time of infection is indicated) will be carried out after official unblinding of the trial, or will be carried out exclusively on specific groups (or other clearly defined subgroups) after these are unblinded. Alternatively, prior to unblinding, these analyses can be performed in a completely blinded manner (e.g. tables with only a single column pooling all regimens).

5.8.1.1. Parameters

The following humoral immune responses may be measured (Table 5). However, not all assays might be available for all immunogenicity analyses covered by this SAP. Some of the exploratory immunogenicity endpoints mentioned in this section will only be considered as potential assessment for post-hoc analysis after the primary analysis is performed, as described in Section 1.1. Further information on which assays will be analyzed in each of the analyses, will be included in the corresponding DPS documents.

Table 5: Summary of Humoral Immunogenicity Assays

Assay	Purpose
Supportive of primary endpoints (Either S-ELISA or VNA will be used to support the primary endpoint)	
SARS-CoV-2 binding antibodies (ELISA)	Analysis of antibodies binding to the SARS-CoV-2 S protein
SARS-CoV-2 neutralization (VNA)	Analysis of neutralizing antibodies to wild-type virus and/or pseudovirion expressing S protein
Supportive of secondary/exploratory endpoints	
SARS-CoV-2 binding antibodies (ELISA)	Analysis of antibodies binding to the SARS-CoV-2 S protein, or SARS-CoV-2 variant proteins
SARS-CoV-2 neutralization (VNA)	Analysis of neutralizing antibodies to wild-type virus and/or pseudovirion expressing S protein, or SARS-CoV-2 variants
SARS-CoV-2 binding antibodies (ELISA and/or SARS-CoV-2 immunoglobulin assay)	Analysis of antibodies binding to the SARS-CoV-2 N protein
Binding antibodies (ELISA) or Ig assay detecting coronavirus-specific antibodies to other coronaviruses	Analysis of antibodies binding to coronaviruses other than SARS-CoV-2
Adenovirus neutralization (neutralization assay)	Analysis of neutralizing antibodies to adenovirus
SARS-CoV-2 binding antibodies to S protein, N protein, RBD of S-protein, and other surface proteins of coronaviruses (MSD)	Analysis of antibodies to S, N, and the RBD of the SARS-CoV-2 S protein, and surface proteins of other coronaviruses
Functional and molecular antibody characterization	Analysis of antibody characteristics including, but not limited to avidity, Fc-mediated viral clearance, Fc characteristics, Ig subclass, IgG isotype, antibody glycosylation, and assessment of antibody repertoire
Epitope-specificity characterization	Analysis of site-specificity, epitope mapping
Cytokine profiling	Analysis of cytokines, chemokines, and other proteins of the innate or adaptive immune response in the serum or plasma
Passive transfer	Analysis of immune mediators correlating with protection against experimental SARS-CoV-2 challenge in a suitable animal model

ELISA = enzyme-linked immunosorbent assay; Fc = crystallizable fragment; Ig = immunoglobulin; SARS-CoV-2 = severe acute respiratory syndrome coronavirus-2; MSD = Meso Scale Diagnostics, LLC; RBD = receptor binding domain; VNA = virus neutralization assay

